10.4.3 Analysis of Other Endpoint(s)

Time to failure - intra-operative repair failure will be defined as just an event.

- If adequate data is available, Kaplan Meier survival estimate for the entire sample, by device implanted and position will be used in this study survival analyses and a Cox model will also be explored adjusting for device implanted and position.
- Available data will be summarized and summary statistics tabulated.

Study Protocol—Device	 smith&nephew
Prospective, Multicenter, Post-Market Clinical Follow-up Study to evaluate safety and performance of the SUTUREFIX ULTRA and SUTUREFIX CURVED Suture Anchors in shoulder and hip arthroscopic repair	Number: 17-5010-06
	Version: 1.0, 09/MAY/2018
	Page: Page 50 of 87

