8.3 STUDY ENDPOINTS

8.3.1 Primary Endpoint

- Clinical success rate, defined as subjects without signs of failure and/or re-intervention at 6 months, as assessed by the surgeon

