8.3.2 Secondary Endpoints

- Clinical success rate, defined as subjects without signs of failure and/or re-intervention at 12 months, as assessed by the surgeon
- Intra-operative anchor deployment success rate
- Number of anchors pulled out
- Use of additional anchors as a result of intra-operative failure
- Device-related re-intervention
- Safety evaluation at all time points
- Post-operative clinical success rate and performance assessed with subject reported outcomes as follows:

All subjects:

- Subject pain assessment with VAS at 6 months* and 12 months*
- Subject satisfaction assessment with VAS at 6 months* and 12 months*
- EQ-5D Questionnaire at 6 months* and 12 months*

Suturefix Ultra Suture Anchor Suturefix Curved Suture Anchor	
Prospective, Multicenter, Post-Market 1 year Clinical Follow-up Study to evaluate safety and performance of the SUTUREFIX ULTRA and SUTUREFIX CURVED Suture Anchors in shoulder and hip arthroscopic repair	Number: 17-5010-06 Version: 1.0, 09/MAY/2018 Page: Page 36 of 87

Hip subjects:

- Hip Outcome Score Activities of Daily Living (HOOS-ADL) at 6 months* and 12 months*
- Modified Harris Hip Score (HHS) at 6 months* and 12 months*

Shoulder subjects:

- ROWE Shoulder Scores at 6 months* and 12 months*
- ASES Shoulder Scores at 6 months* and 12 months*
- Constant-Murley Shoulder Scores at 6 months* and 12 months*

** Patient Reported Outcomes (PROs) are optional and used according to the surgeon's preference*

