9. STUDY PROCEDURES

9.1 VISITS AND EXAMINATIONS

9.1.1 Summary

For a summary of the required procedures by visit, refer to Table 9.1-1: Study Procedures by Visit

Table 9.1.1-1: Study Procedures by Visit

Schedule of events (*as needed)	Visit 1	Visit 2	Visit 3 Visit	Visit 4 Telephone Call or Visit	Visit 5 Unscheduled Visit
	Pre-Operative	Operative through Discharge	6 Months (± 1 M)	12 Months (± 1 M)	
Informed Consent	√				
Inclusion/Exclusion Criteria	√				
Demographics/ Medical History	√				
Intra-op failure as assessed by the surgeon		√			
Operative through Discharge		√			
Post-op Repair failure			√	√	√
All subjects					
Pain assessment with VAS	√**		√**	√**	√**
Satisfaction assessment with VAS	√**		√**	√**	√**
EQ-5D questionnaire	√**		√**	√**	√**
Hip					
HOOS-ADL score	√**		√**	√**	√**
Mod. Harris Hip score	√**		√**	√**	√**
Shoulder					
ROWE score	√**		√**	√**	√**
ASES score	√**		√**	√**	√**

Study Protocol—Device	
Prospective, Multicenter, Post-Market Clinical Follow-up Study to evaluate safety and performance of the SUTUREFIX ULTRA and SUTUREFIX CURVED Suture Anchors in shoulder and hip arthroscopic repair	Number: 17-5010-06
	Version: 0.17, 17/APR/2018
	Page: Page 38 of 87

Schedule of events (*as needed)	Visit 1	Visit 2	Visit 3 Visit	Visit 4 Telephone Call or Visit	Visit 5 Unscheduled Visit
	Pre-Operative	Operative through Discharge	6 Months (± 1 M)	12 Months (± 1 M)	
Constant-Murley score	√**		√**	√**	√**
MRI / Imaging	√		√*	√*	√*
Adverse Event Assessment		√		√	
End of Study/Exit				√	

* If needed to investigate repair failure

** Patient Reported Outcomes (PROs) are optional and used according to the surgeon's preference

Study Protocol—Device	
Prospective, Multicenter, Post-Market Clinical Follow-up Study to evaluate safety and performance of the SUTUREFIX ULTRA and SUTUREFIX CURVED Suture Anchors in shoulder and hip arthroscopic repair	Number: 17-5010-06
	Version: 1.0, 09/MAY/2018
	Page: Page 39 of 87

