10.4 EFFICACY ANALYSIS

10.4.1 Analysis of Primary Endpoint

Clinical success rate, defined as subjects without a signs of failure and/or re-intervention at 6 months, surgeon assessment:

Study Protocol—Device	
Prospective, Multicenter, Post-Market Clinical Follow-up Study to evaluate safety and performance of the SUTUREFIX ULTRA and SUTUREFIX CURVED Suture Anchors in shoulder and hip arthroscopic repair	Number: 17-5010-06
	Version: 1.0, 09/MAY/2018
	Page: Page 47 of 87

- The frequency of the subjects without a signs of failure and/or re-intervention at 6 months together with percentage with a 95% CI will be reported. Clinical success rate for the entire sample, by device implanted (SUTUREFIX ULTRA and SUTUREFIX CURVED) as well as the position, i.e. the hip or the shoulder will be reported. A binary variable of success/failure will be used to fit a logistic model adjusting device implanted and position to estimate the odds ratio of success if data allows.

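### The only event that section 10.4.3 names for time to failure is intra-operative repair failure, which can occur only at surgery, so the event set, dating and censoring need to be stated

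*Combined protocol and SAP*

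**What the plan says.** Section 10.4.3 opens with "Time to failure - intra-operative repair failure will be defined as just an event". It then sets out the method: "Kaplan Meier survival estimate for the entire sample, by device implanted and position will be used in this study survival analyses", with a Cox model to be explored on the same two factors. Both are conditional, in the plan's words, "If adequate data is available". The section gives no other event, no time origin, no rule for dating a failure and no censoring rule.

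The schedule in section 9.1.1 keeps two kinds of failure apart. The row "Intra-op failure as assessed by the surgeon" is ticked at Visit 2 only (operation through discharge). The row "Post-op Repair failure" is ticked at Visits 3, 4 and 5 (6 months, 12 months, unscheduled).

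The primary endpoint in section 8.3.1 is "Clinical success rate, defined as subjects without signs of failure and/or re-intervention at 6 months, as assessed by the surgeon". Section 10.4.1 reports it as a frequency and percentage with a 95% CI, and section 10.4.2 does the same at 12 months. Neither the endpoint nor its analysis says whether a failure during surgery counts. Section 8.3.2 also lists "Use of additional anchors as a result of intra-operative failure" as a separate secondary endpoint.

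**The concern.** An event that can happen only in theatre has no distribution over follow-up. If it is the only event, a survival curve says nothing about how long the repair lasts, although the objective in section 5.1 covers 12 months after arthroscopy. The 6- and 12-month success rates are binary summaries, so this is the only planned analysis that can use when failures occur.

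A second difficulty arises if intra-operative failures are pooled with later ones. The curve and the success rates would then appear in one report under the word failure, without a statement that they count the same subjects. Study treatment is open-label and the fuller SAP announced in section 10 is not among the documents, so the event could end up being chosen after failures are known.

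**Working it through.** **The plan's own figure.** No number is attached to time to failure. The only design figure is in section 11: with 40 subjects and a success rate of 89%, an interval of 78 to 100 with 55% probability. Summing Binomial(40, 0.89) over the outcomes whose exact (Clopper-Pearson) 95% interval has half-width at most 0.11 gives 54.7%, which reproduces it. It does not depend on the event definition in 10.4.3.

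**When the events can occur.**

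| Item | Collected at | Possible event time |
|---|---|---|
| Intra-operative failure | Visit 2 | Day 0 only |
| Post-operative repair failure | Visits 3, 4, 5 | Any time after surgery |

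The post-operative row is not ticked at Visit 2, although that visit runs to discharge and section 9.1.3 provides there for imaging in case of repair failure. The schedule therefore has no post-operative failure tick for the interval between the end of surgery and discharge.

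**Reading 1: intra-operative failure is the only event.** Let q be the intra-operative failure rate. All event times are 0, so the Kaplan-Meier estimate is S(t) = 1 − q for every t > 0. The documents give no q, so 0 to 10% is assumed. The comparison is with 6-month post-operative success rates of 0.86 (synopsis), 0.89 and 0.93 (both section 11).

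| q (assumed) | S(t), t > 0 | minus 0.86 | minus 0.89 | minus 0.93 |
|---|---|---|---|---|
| 0% | 1.00 | +14 points | +11 | +7 |
| 2% | 0.98 | +12 | +9 | +5 |
| 5% | 0.95 | +9 | +6 | +2 |
| 10% | 0.90 | +4 | +1 | −3 |

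The gap runs from +14 to −3 points. A close match is a coincidence of two unrelated rates. With all event times tied at 0, a Cox model can compare only who failed in theatre and carries no information on time.

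**Reading 2: intra-operative failures are added to later failures.** Without censoring, and if later failure is equally likely with or without an intra-operative failure, the curve at 6 months is (1 − q) × S6, where S6 is the post-operative success rate. At q = 0.05 and S6 = 0.89 this is 0.95 × 0.89 = 0.8455.

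- If clinical success also counts intra-operative failures, the two figures are equal.
- If it counts only post-operative failures, the curve is lower by 0.89 − 0.8455 = 0.0445, about 4.5 points.
- If q = 0, there is no gap.

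**Constructed example.** Assume 80 subjects, 4 intra-operative failures, 9 other subjects with a post-operative failure by 6 months, and no dropout.

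| Quantity | Result |
|---|---|
| Curve, reading 1, day 0 to 12 months | 76/80 = 0.950, flat; the 9 later failures are ignored |
| Curve, reading 2, day 0 | 76/80 = 0.950 |
| Curve, reading 2, 6 months | 67/80 = 0.8375 |
| Clinical success, post-operative failures only | 71/80 = 0.8875 |
| Clinical success, all failures | 67/80 = 0.8375 |

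The gap between the reading 2 curve and the post-operative-only rate is 5 points here (4/80), because no subject has both kinds of failure.

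**The case against.** The opening sentence of 10.4.3 is ambiguous. The word *just* can mean that an intra-operative failure is recorded as an event without a meaningful time, while later failures supply the times that the label promises. On that reading the curve falls over follow-up. A reader might infer from the section that the survival analysis cannot show durability at all; the text does not support that, because it does not exclude later failures.

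A reader might also infer that the curve must contradict the 6- and 12-month success rates. That does not follow either. The primary endpoint does not restrict failure to the post-operative period; the restriction is only suggested by the row labels in the schedule. If the rate and the curve count the same failures, they coincide when there is no censoring. Likewise, no section says that an anchor replaced during an otherwise completed operation is a repair failure, so it cannot be assumed that such a subject is a failure in one analysis and a success in another.

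The stakes are limited. Time to failure is not listed in section 8.3, is conditional on adequate data, and belongs to an exploratory study with a fuller SAP still to come. Later failure is also reported through the two success rates and device-related re-intervention.

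All of this stands, and it limits the claim. It does not supply the missing definition: the one event that is named can occur only at surgery, and a programmer who follows the sentence literally obtains a flat line.

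**Conclusion.** The point holds as a defect of definition in a subsidiary analysis, and it should be corrected before the SAP is finalised. On the literal reading the curve is a single drop to 1 − q on day 0 and later failures are not events. On the pooled reading the curve is informative, but it may lie below the success rate by about q × S6: nothing if there are no intra-operative failures, about 4.5 points at q = 5% and S6 = 0.89. These sizes rest on assumed intra-operative rates, no dropout and, for the 4.5 points, a later failure rate that does not depend on intra-operative failure. The primary estimate and the sample size do not change.

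**What to change.** Rewrite section 10.4.3 along these lines: *Time to failure runs from surgery to the first post-operative repair failure or re-intervention at any time after the end of surgery, including before discharge and at unscheduled visits. The event date is used; if it is unknown, the date of the visit at which the failure was found. Subjects without an event are censored at last contact. Intra-operative failure is reported as a proportion. One sensitivity curve counts it as an event on day 0.*

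In sections 10.4.1 and 10.4.2, add one sentence stating whether an intra-operative failure counts against clinical success, so that the curve and the rates can be compared. The primary endpoint needs no other change.

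The cost is one extra sensitivity output and a CRF field for the date of failure or re-intervention, including any before discharge. One limit remains: the 6-month visit has a window of one month either way, so a failure dated by a late visit can fall after the 6-month mark on the curve while counting in the 6-month rate. A footnote giving the number of failures dated by visit would cover this.

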10.5 SAFETY ANALYSES

Adverse events

- Adverse Events (as defined in Safety Reporting Section – All adverse events will be tabulated classified by seriousness and given by frequency and percentages for the entire sample and by device implanted (SUTUREFIX ULTRA and SUTUREFIX CURVED)).

10.6 INTERIM ANALYSES

No interim analysis is foreseen.

11. SAMPLE SIZE JUSTIFICATION

A systematic review by Erickson et al (2015) suggests that the variation in the success rate among patients who have undergone any Suture Anchors for arthroscopic instability repair range from 71-97%. Two studies Lafosse et al (2008) and Thal et al (2007)²⁶ have failure rates of 11.4% and 6.9% within a period of 2 years from surgery, giving success rates of about 87% and 93% respectively suggest that building a 11% confidence interval either side of 89% will ensure that the estimated success rate is within literature extrapolated success rates.

This study considers the SUTUREFIX ULTRA and SUTUREFIX CURVED Suture Anchors for arthroscopic repair success rate and a sample of 80 (40 per device) subjects is considered. A sample size of 40 subjects will estimate a success rate of 89% with a 95% confidence interval (CI) [78: 100] with 55% probability.

Study Protocol—Device	
Prospective, Multicenter, Post-Market Clinical Follow-up Study to evaluate safety and performance of the SUTUREFIX ULTRA and SUTUREFIX CURVED Suture Anchors in shoulder and hip arthroscopic repair	Number: 17-5010-06
	Version: 1.0, 09/MAY/2018
	Page: Page 51 of 87

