2. SYNOPSIS

Title of Study:	Prospective, Multicenter, Post-Market 1 year Clinical Follow-up Study to evaluate safety and performance of the SUTUREFIX ULTRA and SUTUREFIX CURVED Suture Anchors in shoulder and hip arthroscopic repair
Study Design:	
 • Prospective • Approximately 8 sites: 
 - 4 sites for hip group - 4 sites for shoulder group • Two-arms (hip and shoulder)
Study Type:	Post-market study
Study Product:	SUTUREFIX ULTRA and SUTUREFIX CURVED Suture Anchor
Study Purpose:	Prospective, multicenter, post-market clinical follow-up to support CE Mark certification and Notified Body (BSI) for the Shoulder and Hip repair indications. Data to confirm safety and performance levels acceptable for the risk benefit profile of the devices.
Primary Objective:	To demonstrate the performance of the SUTUREFIX ULTRA and SUTUREFIX CURVED Suture Anchors in hip and shoulder for arthroscopic treatment over a time period of 6 months after arthroscopy.
Secondary Objective:	To assess safety and performance, supporting the use of SUTUREFIX ULTRA and SUTUREFIX CURVED Suture Anchors in hip and shoulder arthroscopy repair.
Statistical Rationale:	The study sample was decided based on the feasibility of recruitment, enrolment and follow-up considerations. The study is therefore not powered for any statistical testing but will be able to estimate a success rate of 86% with a 95% confidence interval (CI) [75: 97]. Previous studies suggest that the success rate among patients who have undergone any Suture Anchors for arthroscopic

Suturefix Ultra Suture Anchor	
Suturefix Curved Suture Anchor	
Prospective, Multicenter, Post-Market 1 year Clinical Follow-up Study to evaluate safety and performance of the SUTUREFIX ULTRA and SUTUREFIX CURVED Suture Anchors in shoulder and hip arthroscopic repair	Number: 17-5010-06
	Version: 1.0, 09/MAY/2018
	Page: Page 5 of 87

	instability repair is 71-97%.
Sample Size:	A total of 80 subjects; 40 subjects for the shoulder group and 40 subjects for the hip group, will receive at least one device, SUTUREFIX ULTRA and/or SUTUREFIX CURVED Suture Anchor. A sample size of 40 subjects will estimate a success rate of 89% with a 95% confidence interval (CI) [78: 100] with 55% probability.
Number of Study Sites:	Approximately 8 sites: 
 • 4 sites for study hip group • 4 sites for study shoulder group
Targeted Global Regions:	Europe

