6. INVESTIGATIONAL PRODUCT(S)

6.1.1 Investigational Products

The SUTUREFIX Anchor is offered in multiple suture configurations including single and double loaded suture options. The delivery system of these anchors enables the suture implant to be placed in the bone in an un-deployed state. During anchor deployment, tension is applied to the repair sutures. The tension applied to the repair sutures, which are threaded through the anchor suture, cause the anchor suture to bunch up. In its deployed state the anchor has a larger nominal diameter than the hole in which it is inserted, locking it into the bone tunnel (Figure 1). The implanted suture anchor construct retains mechanical stability of the soft tissue to bone construct during the healing period. The anchors are available preloaded with either one #2 suture or two #1 sutures.

Suturefix Ultra Suture Anchor Suturefix Curved Suture Anchor	
Prospective, Multicenter, Post-Market 1 year Clinical Follow-up Study to evaluate safety and performance of the SUTUREFIX ULTRA and SUTUREFIX CURVED Suture Anchors in shoulder and hip arthroscopic repair	Number: 17-5010-06 Version: 1.0, 09/MAY/2018 Page: Page 24 of 87

The anchor suture is composed of a single strand of #5 braided, silicone-coated, polyester, non-absorbable suture marketed under the trade name DURABRAID™. The repair suture is comprised of non-absorbable, uncoated ultra-high molecular weight polyethylene (UHMWPE) marketed under the trade name ULTRABRAID™.

Figure 1. SUTUREFIX Implant

Figure 2. SUTUREFIX ULTRA

Figure 3. SUTUREFIX ULTRA DRILL

The SUTUREFIX ULTRA Suture Anchor consists of three components; an all suture based implant preloaded onto a rigid insertion device (Figure 2 and 3), hole preparation and insertion accessory instruments. The Smith & Nephew SUTUREFIX CURVED Suture Anchor utilizes the same anchor as the SUTUREFIX ULTRA (Figure 1), however it comes preassembled to a flexible insertion device (Figure 4 and 5). These devices are provided sterile, for single use only.

[figure not shown]

Figure 4. SUTUREFIX CURVED

Figure 5. SUTUREFIX CURVED DRILL

The instruments included in this file consist of single-use sterile drills (rigid and flexible), as well as reusable drill guides (straight and curved) and obturators (rigid and flexible) (examples seen below in Figures 4 and 5).

Figure 6. Straight obturator and twist drill

Figure 7. Curved Drill Guide

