7. SUBJECT ENROLLMENT AND WITHDRAWAL

7.1 SUBJECT POPULATION

In this study a minimum of 80 subjects will be enrolled, 40 subjects for each group, hip and shoulder. The subjects will be treated with the study device(s) for hip or shoulder instability.

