7.4 SCREENING

To eliminate the potential for selection bias, Investigators should consecutively pre-screen all subjects undergoing arthroscopic instability repair with SUTUREFIX ULTRA Suture Anchor and/or SUTUREFIX CURVED Suture Anchor. Subjects receiving care at the investigative sites will be pre-screened as potential subjects for the study. To do so, only the existing information obtained per standard routine medical procedures will be used. No study-specific screening procedures, activities or questionnaires will be performed during pre-screening.

Participating study sites are required to document all screened subjects considered for inclusion in this study. If a subject is excluded from the study, the reasons for exclusion will be documented in the subject's source documents and noted on the Screening and Enrollment Log.

Suturefix Ultra Suture Anchor Suturefix Curved Suture Anchor	
Prospective, Multicenter, Post-Market 1 year Clinical Follow-up Study to evaluate safety and performance of the SUTUREFIX ULTRA and SUTUREFIX CURVED Suture Anchors in shoulder and hip arthroscopic repair	Number: 17-5010-06 Version: 1.0, 09/MAY/2018 Page: Page 31 of 87

Once a subject has completed the informed consent procedure and signed an Ethics Committee approved Informed Consent Form (ICF), the PI or delegated study research staff can complete the screening process with the subject (see Section 9.1).

All screening activities which occur prior to consent shall be referred to as pre-screening.

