8. STUDY DESIGN

8.1 STUDY DESIGN

[figure not shown]
This is a prospective, multicenter study to evaluate the clinical and intraoperative outcomes from 80 subjects implanted with the SUTUREFIX ULTRA and/or SUTUREFIX CURVED Suture Anchors in hip or shoulder groups. Up to 8 sites (up to 4 sites for study hip group and up to 4 sites for study shoulder group) in Europe will participate in the study. Data from eligible subjects, who have provided written and informed consent for the collection of their coded data (see section 9.1.2-9.1.6) will be recorded from the subject medical file on Case Report Forms (CRFs). Follow-up clinical assessments will be performed at 6 months and 1 year post-operatively.

Suturefix Ultra Suture Anchor Suturefix Curved Suture Anchor Prospective, Multicenter, Post-Market 1 year Clinical Follow-up Study to evaluate safety and performance of the SUTUREFIX ULTRA and SUTUREFIX CURVED Suture Anchors in shoulder and hip arthroscopic repair	 Number: 17-5010-06 Version: 1.0, 09/MAY/2018 Page: Page 34 of 87
---	--

This is an open-label study with consecutive enrollment. The study will continue for 12 months from the date of treatment for the last subject completing the study as planned. Only subjects who meet the enrollment criteria as listed in section 7 will be enrolled into the study. The study duration is planned for 24 months.

The data will support CE Mark certification for the Shoulder and Hip repair indications. The data should confirm safety and performance levels acceptable for the risk benefit profile of this device.

Figure 8.1-1: Study Flowchart

Suturefix Ultra Suture Anchor	
Suturefix Curved Suture Anchor	
Prospective, Multicenter, Post-Market 1 year Clinical Follow-up Study to evaluate safety and performance of the SUTUREFIX ULTRA and SUTUREFIX CURVED Suture Anchors in shoulder and hip arthroscopic repair	Number: 17-5010-06
	Version: 1.0, 09/MAY/2018
	Page: Page 35 of 87

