8.2 ALLOCATION AND BLINDING

This study is an open-label study with consecutive enrolment without randomization. There is no control group. Although there are two groups one hip and one shoulder group blinding of the surgeon is not applicable due to the different indications and product specificities. The evaluator will be blinded to the treatment groups.

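### Section 11 sizes the study as 40 subjects per device, but the design fixes 40 per joint and nothing secures 40 for either device

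*Combined protocol and SAP*

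**What the plan says.** Section 11 gives the sample as "a sample of 80 (40 per device) subjects is considered" and follows it at once with the precision statement for 40 subjects: 89% success, 95% CI 78 to 100, 55% probability.

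Other sections count the 40 differently:

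- **Synopsis, Sample Size:** "40 subjects for the shoulder group and 40 subjects for the hip group, will receive at least one device, SUTUREFIX ULTRA and/or SUTUREFIX CURVED". The identical precision statement comes directly after.
- **Section 7.1:** "80 subjects will be enrolled, 40 subjects for each group, hip and shoulder".
- **Section 8.1:** "80 subjects implanted with the SUTUREFIX ULTRA and/or SUTUREFIX CURVED Suture Anchors in hip or shoulder groups". Sites are also divided by joint, up to four for hip and up to four for shoulder.
- **Section 7.4:** the subjects pre-screened consecutively are those undergoing "arthroscopic instability repair with SUTUREFIX ULTRA Suture Anchor and/or SUTUREFIX CURVED Suture Anchor".
- **Section 8.2:** "This study is an open-label study with consecutive enrolment without randomization".

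The analysis treats device and joint as separate factors. Section 10.4.1 reports "Clinical success rate for the entire sample, by device implanted (SUTUREFIX ULTRA and SUTUREFIX CURVED) as well as the position", meaning hip or shoulder, and puts both factors in one logistic model.

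**The concern.** Joint and device are different groupings, so per device cannot be shorthand for per joint. A reader of Section 11 would take the n=40 precision as holding for ULTRA and for CURVED separately. The design fixes 40 only for hip and for shoulder. How many subjects receive each device depends on what surgeons use in consecutive cases.

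A second gap follows from the first. A subject may receive both devices, and no section says how that subject is classified. The by-device denominators are therefore undefined: such a subject could be counted twice, left out, or assigned to one device. The device groups need not add up to 80. By-device results are planned for the primary endpoint, nearly all secondary endpoints, time to failure and adverse events (Sections 10.4.1 to 10.5), so the gap runs through most of the analysis. The detailed SAP is due only before database lock (Section 10), so a rule left open now could be chosen once data have been seen.

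**Working it through.** **Inputs from the protocol (Section 11 and synopsis).** n = 40; true success rate p = 0.89; target half-width 0.11 (89 ± 11 gives 78 to 100); stated probability 55%.

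**Step 1: reproduce the stated 55%.** Let X ~ Binomial(40, 0.89), and sum the probabilities of all X whose exact (Clopper-Pearson) 95% CI has half-width at most 0.11.

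- 35/40: CI 0.732 to 0.958, half-width (0.958 − 0.732)/2 = 0.113. This misses the target.
- 36/40: CI 0.763 to 0.972, half-width (0.972 − 0.763)/2 ≈ 0.104. This meets it, and larger X are narrower still.
- Outcomes at the far low end also give narrow intervals, but their probability at p = 0.89 is negligible.
- Result: P(X ≥ 36) = 0.547, against 55% stated.

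The figure reproduces. It is a property of any group of 40, so it holds for each joint as enrolled.

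**Step 2: does the design produce 40 per device?**

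| Feature | By joint | By device |
|---|---|---|
| Enrolment target | 40 hip, 40 shoulder (synopsis, 7.1) | Only the parenthesis in Section 11 |
| Sites divided | Yes (synopsis, 8.1) | No |
| Quota, stratum or allocation | Fixed numbers per group | None found |
| Groups mutually exclusive | Yes | No, both devices allowed |

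Forty per device could occur, but nothing in the plan makes it occur.

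**Step 3: precision if the split is uneven.** The documents give no device mix, so the group sizes below are assumptions. The method is that of Step 1. The expected half-width is the exact half-width averaged over Binomial(n, 0.89).

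| Subjects with the device | Expected exact half-width (points) | P(half-width ≤ 11 points) |
|---|---|---|
| 10 | 21.6 | 0.00 |
| 20 | 15.1 | 0.10 |
| 30 | 12.2 | 0.34 |
| 40 | 10.5 | 0.55 |
| 50 | 9.4 | 0.91 |
| 60 | 8.5 | 0.99 |
| 70 | 7.9 | 1.00 |

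Without overlap, the rows pair as 30/50, 20/60 and 10/70, with either device as the smaller group. At n = 20 only 20/20 successes meets the target. Its lower limit is 0.025^(1/20) = 0.832, so the half-width is (1 − 0.832)/2 = 0.084, and its probability is 0.89^20 = 0.097.

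**Step 4: the same observed rate of 90% at three group sizes (exact 95% CI).**

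- 36/40: 76.3% to 97.2%
- 18/20: 68.3% to 98.8%
- 9/10: 55.5% to 99.7%

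**The case against.** The strongest reply is that this is one mislabelled parenthesis. Every other section organises the study by joint, and the synopsis already attaches the precision statement to the joints. The number of subjects was set on feasibility, the study is declared exploratory and unpowered, and there is no by-device hypothesis or threshold. A smaller device group would widen a descriptive interval and reverse no decision. Section 6.1.1 adds that CURVED "utilizes the same anchor as the SUTUREFIX ULTRA" on a different insertion device, so the split should matter less for 6-month success than for the intra-operative endpoints. The handling of subjects with both devices could reasonably be left to the SAP.

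Much of this stands, and it limits the weight of the point. The total and the per-joint estimate are untouched. The splits in the working are illustrations: with enough subjects receiving both devices, both device groups could reach or exceed 40.

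It does not remove the contradiction. In an unpowered study the precision statement is the only quantitative support for the sample size, so the group it describes has to be the right one. Deferring detail to the SAP is normal, but the protocol already commits to by-device results and device-adjusted models without defining the device variable.

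**Conclusion.** The concern holds. Section 11 contradicts the synopsis and Sections 7.1 and 8.1, and the design does not secure 40 subjects per device or the precision claimed for them.

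The n=40 statement itself is correct (54.7% against 55%) and applies to each joint. That is before attrition: 40 is an enrolment number, and the full analysis set in Section 10.2 also requires a post-baseline assessment.

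The size of the by-device shortfall cannot be known from the documents. Assuming an 89% true rate, exact intervals and no overlap, the smaller device group has an expected half-width of 12.2, 15.1 or 21.6 points at 30, 20 or 10 subjects, against 10.5 at 40. The larger group gains precision. The error should be corrected, but it does not threaten the total sample size or the per-joint analysis.

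**What to change.** 1. **Section 11.** Replace the per-device parenthesis with 40 per joint (40 hip, 40 shoulder). State that the precision statement applies to each joint only, as enrolled and before dropout.
2. **Section 10.4 and the SAP.** Define the device variable in advance. One workable choice is ULTRA only, CURVED only, or both, so that each subject is counted once. Report by-device success descriptively, with the actual n and exact 95% CIs. Use the same definition for adverse events (Section 10.5), and state how the device term in the logistic, repeated-measures and Cox models treats subjects with both devices.
3. **Anchor-level endpoints.** Tabulate deployment, pull-out and additional anchors by the device of each anchor, if the CRF records it. This needs to be confirmed.

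The cost is wording in Sections 11 and 10 and in the SAP, plus possibly one CRF field for device type per anchor, which the documents do not show. The drawbacks are that no precision is then promised for either device and that a three-way split makes the cells thinner.

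If 40 per device was really intended, the alternative is an explicit device target with a rule for subjects who receive both. That would change enrolment as well as wording.
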